9.3.9.6. Adverse events of special interest

An AESI is an AE (serious or nonserious) of scientific and medical concern specific to the Sponsor's product or program, for which ongoing monitoring and immediate notification (within 24 hours) by the Investigator to the Sponsor is required. Such events may require further investigation in order to characterize and understand them. Adverse events of special interest may be added, modified, or removed during a study by protocol amendment; they include:

- Pregnancy of a female participant entered in a study and received at least one dose of the IMP as well as pregnancy occurring in a female partner of a male participant entered in a study with IMP;
 - Pregnancy occurring in a female participant entered in the clinical trial or in a female partner of a male participant entered in the clinical trial will be qualified as an SAE only if it fulfills one of the seriousness criteria (see [Appendix 12](#)).
 - In the event of pregnancy in a female participant, IMP must be discontinued.
 - Follow-up of the pregnancy in a female participant or in a female partner of a male participant is mandatory until the outcome has been determined (See [Appendix 13](#)).
- Symptomatic overdose (serious or nonserious) with IMP

- Increase in ALT $>3 \times$ ULN (See [Appendix 15](#) for follow-up instructions). If such laboratory values have been determined, follow-up within 72 hours of the same value and total bilirubin levels is required and if value is repeated (eg, ALT $>3 \times$ ULN), such value shall be reported as well together with the repeated total bilirubin values and any other laboratory values to determine the cause of the initially determined ALT increase.
- Any Grade 4 or 5 infection where the participant is hospitalized ≥ 24 hours and/or requires emergency care and/or requires intravenous antibiotics.
- Any occurrence of uveitis (including Vogt-Koyanagi-Harada disease [VKHD])

9.3.9.7. Guidelines for reporting product complaints

Any defect in the IMP must be reported as soon as possible by the Investigator to the monitoring team that will complete a product complaint form within required timelines.

Appropriate information (eg, samples, labels or documents like pictures or photocopies) related to product identification and to the potential deficiencies may need to be gathered. The Investigator will assess whether or not the quality issue has to be reported together with an AE or SAE.

10. STATISTICAL METHODS

A detailed Statistical Analysis Plan (SAP) will be developed and finalized before the study database is locked which will supersede the statistical analysis methods described in the protocol; however, any major modification of the outcome measures and/or its analysis will also be reflected in the clinical study report (CSR).

Descriptive summaries of variables by treatment will be provided where appropriate. Generally, continuous variables will be summarized using the following descriptive statistics: mean, standard deviation, number of observations, median, minimum, and maximum. Summaries will also be presented for the change from baseline, when appropriate. For categorical variables, the counts and proportions of each value will be tabulated by treatment. For time to event variables, point estimates (25th, 50th, and 75th percentiles) along with 95% confidence intervals will be tabulated by treatment using Kaplan-Meier methods. Survival estimates will also be shown graphically for each treatment.

All statistical tests will be two-sided unless otherwise noted.

The pediatric participants will not be tested, and descriptive statistics will be done on these participants. Additional statistical analyses on these pediatric participants may be provided for specific regulatory requests.

10.1. Determination of Sample Size

The adult sample size chosen for this study was selected to achieve enrollment of 129 adult participants (≥ 18 years) on rilzabrutinib and 65 adult participants on placebo. The pediatric sample size of up to 30 participants (20 participants on rilzabrutinib and 10 participants on placebo) was determined based on clinical practice and is adequate to descriptively describe the safety and efficacy in pediatric participants. With a sample size of 20 pediatric participants on rilzabrutinib the maximum width of an exact 90% CI on response rate would be 40%.

A sample size of approximately 194 (129 versus 65 adult participants in the rilzabrutinib versus placebo arms, respectively) will provide 95% power to detect a 20% difference in response rates as defined in the primary endpoint (Section 3.2.1) between the 2 arms (25% vs 5%, in the rilzabrutinib versus placebo arms, respectively), using the Fisher's Exact test with a 0.05 two-sided significance level.

The assumption of a 25% response rate in the rilzabrutinib group is based on the Phase 1/2 study PRN1008-010 Part A (DFI17124 Part A) (durable response [8 out of the last 12 weeks with platelet count at or above 50,000/ μ L in the absence of rescue medication]) and the 5% response rate is estimated based on the observed placebo response in previous randomized controlled trials of ITP medications (Bussel 2018). The participants who are not evaluable for primary efficacy due to dropout or missing data will be considered as non-responders.

10.2. Objectives and Endpoints

Please refer to Section 3.

10.3. Analysis Populations

10.3.1. Safety Population

All participants who are randomized and receive at least one dose of study medication will be included in the Safety Population. The Safety Population is the primary analysis population for safety. Participants will be analyzed according to the treatment they actually received, not necessarily the treatment they were allocated to at randomization. Results for the blinded treatment period will be presented “as treated.” Further details will be provided in the SAP on how data collected during the open-label period will be analyzed.

10.3.2. Intent-to-Treat (ITT) Population

All participants who are randomized will be included in the intent-to-treat (ITT) Population. The ITT Population will be used for efficacy analysis. Participants will be analyzed according to the treatment they were allocated to at randomization; not necessarily the treatment they actually received. Results will be presented “as randomized.”

10.3.3. Modified ITT (mITT) Population

All participants who are randomized and receive at least one dose of study medication will be included in the mITT Population. The mITT Population may be used for sensitivity analysis. Participants will be analyzed according to the treatment they were allocated to at randomization; not necessarily the treatment they actually received. Results will be presented “as randomized.”

10.3.4. Pharmacokinetic (PK) Population

All participants who receive at least one dose of study medication in the safety population and have sufficient data for PK analysis will be included in the PK population.

10.3.5. Disposition of the Study Participants

The disposition of participants will be described with summaries of the number of participants treated and discontinued from the study, including the primary reason for premature discontinuation.

10.3.6. Demographic and Baseline Characteristics

Summaries of participant disposition, demographics, and baseline characteristics will be provided by treatment group.

Demographic and baseline characteristics (age, sex, race, ethnicity, weight, height, and body mass index) will be summarized using descriptive statistics. No formal statistical analyses will be performed, and no inferential statistics reported.

10.3.7. Exposure to Study Treatment

The number of received doses will be summarized by treatment group. Treatment duration and compliance for all participants will be described.

10.3.8. Safety and Tolerability Analysis

Safety will be assessed by the incidence, severity, and relationship of TEAEs, including clinically significant changes in physical examination, laboratory tests, ECG, clinical laboratory test results, and vital signs. AEs will be categorized as treatment-emergent after the first dose of rilzabrutinib has been administered.

The nature, frequency, and severity of AEs, including AESIs, SAEs, and AEs leading to discontinuation will be summarized descriptively by treatment group. AEs possibly related to protocol allowed ITP concomitant medications, TPO- RAs and CS, will be grouped and analyzed separately in addition to the above.

A by-participant TEAE data listing, including verbatim term, preferred term, and system organ class (SOC), treatment, relationship to the study drug and intensity (severity) will be provided.

The number of participants experiencing AEs and number of AEs will be summarized by treatment group using frequency counts.

A change from baseline table will be provided for vital signs and clinical laboratory results by treatment group.

A shift table describing out-of-normal range shifts will be provided for clinical laboratory results, as appropriate.

AEs will be coded using the most current Medical Dictionary for Regulatory Activities (MedDRA®) available at the time of entry and the version will not change through completion of study data available at the Sponsor or designee.

Concomitant medications will be coded using the most current World Health Organization (WHO) drug dictionary and the version will not change through completion of study data available at the Sponsor or designee.

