9.3.4. Adverse Event Relationship to Study Medication

Investigators should use their knowledge of the study participant, the circumstances surrounding the event, and an evaluation of any potential alternative causes to determine whether or not an AE is considered to be related to any study drug (eg, rilzabrutinib or placebo), indicating "yes" or "no" accordingly.

The following guidance should be taken into consideration:

- Temporal relationship of event onset to the initiation of rilzabrutinib or placebo
- Course of the event, considering especially the effects of dose reduction, discontinuation of study medication, or reintroduction of rilzabrutinib or placebo (if applicable)
- Known association of the event with rilzabrutinib or placebo or with similar treatments
- Known association of the event with the disease under study
- Presence of risk factors in the study participant or use of concomitant medications known to increase the occurrence of the event
- Presence of non-treatment-related factors that are known to be associated with the occurrence of the event

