9.3.5. Adverse Event Relationship to Standard of Care Medication

Investigators should use their knowledge of the study participant, the circumstances surrounding the event, and an evaluation of any potential alternative causes to determine whether or not an AE is considered to be related to their standard of care medication (eg, CSs or TPO-RA), indicating "yes" or "no" accordingly. For this study standard of care medications may only be reduced due to a safety concern (eg, a corresponding AE).

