## VERSION HISTORY

This statistical analysis plan (SAP) for study EFC17093/PRN1008-018 is based on the amended protocol 03 dated 11 August 2022 (current protocol). This section summarizes the major changes to the statistical analysis features in the SAP including major changes from the current protocol.

The first participant was randomized on 16 April 2021. This SAP is approved before the early analysis is conducted when the last adult participant has concluded the blinded treatment period (see [Section 3.8](#)).

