### 3.6.2 Adverse events

#### General common rules for adverse events

All AEs will be graded according to National Cancer Institute Common Terminology Criteria for Adverse Events (NCI-CTCAE version 5.0) and coded to a lower-level term (LLT), preferred term (PT), high-level term (HLT), high-level group term (HLGT), and associated primary system organ class (SOC) using the Medical Dictionary for Regulatory Activities (MedDRA) version currently in effect at Sanofi at the time of database lock.

The AEs will be analyzed in the following 2 categories:

- Pre-treatment AEs: AEs that developed, worsened, or became serious during the pre-treatment period.
- TEAEs: AEs that developed, worsened, or became serious during the treatment-emergent periods ([Section 3.1](#))

The primary focus of AE reporting will be on TEAEs. Pre-treatment AEs will be described separately.

An AE with incomplete or missing date/time of onset (occurrence, worsening, or becoming serious) will be classified as a TEAE unless there is definitive information to determine it is a pre-treatment AE.

If the assessment of the relationship to IMP is missing for an AE, this AE will be assumed as related to IMP. If the severity/grade is missing for 1 of the treatment-emergent occurrences of an AE, the severity/grade will be imputed (by treatment-emergent period) with the maximal severity/grade of the other occurrences. If the severity is missing for all the occurrences, the severity/grade will be left as missing.

Multiple occurrences of the same event in the same participant will be counted only once in the tables within an observation period, using the maximum (worst) grade (by treatment-emergent period). Summaries will be provided for all grades combined unless otherwise specified. Missing grades, if any, will be included in the “all grades” category.

The AE tables will be sorted as indicated in [Table 6](#).

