**Table 7 - Analyses of adverse events**

MedDRA levels		DB 12W		DB 24W		OL d	LTE e	DB+OL+LTE f
		Adults	Peds	Adults	Peds	Adults and Peds Separately		
All TEAE	Overview a	✓	✓	✓	✓	✓	✓	✓
	Primary SOC and PT	✓	✓	✓ g	✓ g	✓	✓	✓
	PT			✓				
Common TEAE (≥5% in rilzabrutinib group)	Primary SOC and PT			✓				
	Primary SOC, and PT	✓	✓	✓	✓	✓	✓	✓
	Primary SOC and PT			✓	✓			
TEAE related to IMP as per Investigator's judgment	Primary SOC and PT	✓	✓	✓	✓	✓	✓	✓
TEAE by maximal CTCAE grade	Primary SOC and PT			✓	✓			
Any ≥Grade 3 TEAE	Primary SOC and PT			✓	✓			
Any ≥Grade 3 TEAE related to IMP as per Investigator's judgment	Primary SOC and PT	✓	✓					
Treatment emergent SAE	Primary SOC and PT			✓	✓	✓	✓	✓
Treatment emergent SAE related to IMP as per Investigator's judgment	Primary SOC and PT			✓	✓	✓	✓	✓
TEAE leading to permanent discontinuation of study intervention	Primary SOC and PT			✓	✓	✓	✓	
TEAE leading to death	Primary SOC and PT			✓				✓
Any treatment emergent AESI	PT			✓	✓	✓	✓	

	MedDRA levels	DB 12W		DB 24W		OL d	LTE e	DB+OL+LTE f
		Adults	Peds	Adults	Peds	Adults and Peds Separately		
Any ≥Grade 2 treatment-emergent bleeding event b	PT			✓	✓	✓	✓	
Any ≥Grade 2 treatment-emergent bleeding event b related to IMP as per Investigator's judgement	PT			✓	✓	✓	✓	
Any ≥Grade 2 TEAEs under SOC "Infections and Infestations"	PT			✓	✓	✓	✓	
Any ≥Grade 2 TEAEs under SOC "Infections and Infestations" related to IMP as per Investigator's judgement	PT			✓	✓	✓	✓	
Neutropenia b	PT			✓	✓	✓	✓	
Anemia b	PT			✓	✓	✓	✓	
Thromboembolic events b	PT			✓	✓	✓	✓	
GI events b (analyses below within Section 3.6.2 )	HLT and PT			✓	✓	✓	✓	✓
Covid-19 related TEAEs c	Primary SOC and PT			✓				
Any TEAE by age group (<65, ≥65 years)	Primary SOC and PT			✓				✓
Any TEAE by sex (male, female)	Primary SOC and PT			✓	✓			✓
Any TEAE by concomitant ITP medications (CS, TPO-RA, Both CS and TPO-RA, Neither CS nor TOP-RA)	Primary SOC and PT			✓	✓			✓

MedDRA levels		DB 12W		DB 24W		OL d	LTE e	DB+OL+LTE f
		Adults	Peds	Adults	Peds	Adults and Peds Separately		
Pre-treatment AE	Overview a			✓				
	Primary SOC and PT			✓	✓			
Post-treatment AE	Primary SOC and PT							✓

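### The SAP plans no analysis of AEs attributed to background corticosteroid or TPO-RA, although Protocol 10.3.8 commits to one, and it does not record the omission

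*Protocol*

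**What the plan says.** **Protocol.** Section 9.3.4 asks the investigator for a yes/no judgment on whether an AE is related to study drug. Section 9.3.5 asks a second yes/no question, whether "an AE is considered to be related to their standard of care medication", with CS and TPO-RA as its examples. Section 10.3.8 lists the safety summaries by treatment group and then adds: "AEs possibly related to protocol allowed ITP concomitant medications, TPO- RAs and CS, will be grouped and analyzed separately in addition to the above".

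**SAP.** Section 3.6.2 and Table 7 use relatedness to IMP only, for example "TEAE related to IMP as per Investigator's judgment". The rule for a missing judgment has the same scope: "If the assessment of the relationship to IMP is missing for an AE, this AE will be assumed as related to IMP". The nearest output that involves the background drugs is the Table 7 row that reads "Any TEAE by concomitant ITP medications (CS, TPO-RA, Both CS and TPO-RA, Neither CS nor TOP-RA". As the table reads, that row is ticked for the 24-week double-blind period (adults and pediatrics) and for the cumulative DB+OL+LTE column, but not for the OL or LTE columns.

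**Record of changes.** The SAP version history describes itself this way: "This section summarizes the major changes to the statistical analysis features in the SAP including major changes from the current protocol". SAP 3.9 lists changes made by protocol amendment. Neither mentions the analysis in Protocol 10.3.8.

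**The concern.** CS and TPO-RA carry toxicities of their own. The protocol provides for this by asking for a second attribution and promising an analysis of it. The two questions are separate, so an event can be marked related to IMP, to the background drug, to both, or to neither. If only the IMP answer is tabulated, an infection that the investigator links to both rilzabrutinib and a steroid stands in the IMP-related infection row with no sign of the second attribution. An event linked only to the background drug is not identified anywhere.

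The matter weighs most in the open-label period and the LTE. All participants then receive rilzabrutinib, so there is no randomized comparator. In the LTE, background drugs may also be tapered, withdrawn, restarted or newly started (Protocol Section 4). The question is not academic for this programme: Protocol Table 4 describes serious infection cases as confounded by underlying disease and/or high-dose corticosteroid treatment.

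**Working it through.** No figure in the plan needs reproducing. The check sets the commitment beside the planned outputs.

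**1. Relatedness rows in SAP Table 7.**

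| Row concerns | Related to IMP | Related to CS/TPO-RA |
|---|---|---|
| All TEAE | yes | no |
| Grade 3 or higher TEAE | yes | no |
| SAE | yes | no |
| Grade 2 or higher bleeding | yes | no |
| Grade 2 or higher infection | yes | no |
| Total rows | 5 | 0 |

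The overview list in SAP 3.6.2 and the extra analyses of infection, bleeding and gastrointestinal events after Table 8 likewise refer to IMP only. The by-participant listing in Protocol 10.3.8 names only relationship to study drug. No specified output uses the answer to the 9.3.5 question.

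**2. What the IMP-related tables can and cannot show.** For any set of events, let a be the number related to IMP only, b to both, c to CS/TPO-RA only, and d to neither.

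- Planned: a + b (the IMP-related events) and a + b + c + d (all TEAEs).
- Not recoverable: b and c, because two totals do not determine them.
- With a table of CS/TPO-RA-related events (b + c) and a count of those also marked IMP-related (b): c = (b + c) − b, a = (a + b) − b, and d is the remainder.

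This subtraction is exact for event counts. Table 7 mainly counts participants with at least one event, and one participant can fall in several groups. The count of those marked related to both should therefore be reported directly.

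**3. Whether the split by concomitant medication replaces the analysis.** It differs in three ways.

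- *Unit.* It groups participants by drug taken. A steroid user's event attributed to rilzabrutinib and another steroid user's event attributed to the steroid fall in the same column.
- *Scope.* It covers any TEAE, not related TEAEs.
- *Period.* It is planned for DB 24W and cumulatively. The IMP-related TEAE and SAE rows are also ticked for OL and LTE.

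**4. Whether the commitment predates the SAP.** The SAP says it is based on amended protocol 03. The change logs for amendments 04 and 05 list no edit to Section 10.3.8. The current protocol (amendment 05, 15 May 2024) is dated after SAP version 3 (18 March 2024) and still carries the commitment. That the text was already there when the SAP was written is an inference from the logs.

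**The case against.** The strongest reply has five parts.

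- **The IMP judgment already weighs background drugs.** Protocol 9.3.4 tells the investigator to consider concomitant medications that raise the risk of the event, and Appendix 12.3 names concomitant therapy among alternative causes. This stands. A reader might infer that the IMP-related tables cannot be separated from background-drug toxicity. The documents do not support that: IMP relatedness is its own judgment. The gap is limited to events marked related to both and events attributed to CS/TPO-RA alone.
- **The placebo arm helps.** Background drugs are permitted in both arms at stable doses, so the double-blind comparison bears on what rilzabrutinib adds. This stands for that period. It does not count attributed events, and it has no counterpart in OL or LTE.
- **The Table 7 split may be the SAP's way of meeting 10.3.8.** Section 10.3.8 does not cite the 9.3.5 question, so this is possible. But the promised grouping is of AEs by possible relation to the drugs, and a split by drug taken does not provide it. If substitution was intended, the SAP should say so.
- **The omission may not need recording.** Protocol Section 10 lets the SAP supersede the protocol's methods, and the SAP's change records are limited to major changes. Whether a supplementary descriptive analysis is major is a matter of judgment. Against that, the protocol synopsis says the SAP will attend to changes of substance, and a stated safety analysis with no SAP counterpart reasonably falls under that.
- **The data may not exist in usable form.** The eCRF is not in the documents, and Appendix 12.3 asks about causality for the study intervention only. This stands as a condition on the fix.

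**Conclusion.** The point holds as an unrecorded omission. The protocol commits to a grouped analysis of AEs possibly related to CS and TPO-RA and asks investigators for the attribution. The SAP plans relatedness outputs for IMP only, and its one table by background medication is by exposure rather than attribution. No planned output shows events attributed to CS/TPO-RA, alone or with IMP, in any period.

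The consequence is moderate. Safety analyses are descriptive with no testing (SAP 3.6), so no endpoint, error rate or efficacy comparison changes. The effect is on interpretation of the safety tables, most in OL and LTE.

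A reader might want to put a share on the IMP-related events that carry a second attribution. The documents give no basis for one, so none is offered. Nor do they promise a full four-way classification across event groups; its absence is not a defect.

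The conclusion rests on Table 7 as extracted, on the inference from the amendment logs, and on the assumption that the 9.3.5 answer is captured in the eCRF.

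**What to change.** Add two rows to SAP Table 7: TEAEs, and treatment-emergent SAEs, related to CS and/or TPO-RA in the investigator's judgment, by primary SOC and PT. Present DB 24W by arm, and OL and LTE as single-group summaries. In each, report the number also marked related to IMP. State how a missing CS/TPO-RA judgment is handled, since the present rule covers IMP only. If the sponsor prefers to rely on the split by concomitant medication, the SAP should record that it replaces the Protocol 10.3.8 analysis and give the reason.

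Cost: 2 event types × 3 periods × 2 age groups = 12 descriptive tables, because Table 7 reports adults and pediatrics separately, plus a few lines of SAP text. Protocol 9.3.5 already asks for the data; confirm the eCRF field first.
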